During the double-blind treatment period (between Visit 2 and Visit 4), participants will have up to 60 days to treat 2 qualifying prodrome events, as defined above, with study intervention. Participants should treat as soon as they are confident that a headache will inevitably follow their prodrome symptoms.

eDiary Assessments

During both the screening and double-blind treatment periods, the participant will report information in the eDiary at the time of each qualifying prodrome event:

- Confirmation that the participant is experiencing a qualifying prodrome event
- Identification and intensity of individually specific prodrome symptom(s)
- Headache pain and intensity (if it occurs)
- Nonheadache symptoms (photophobia, phonophobia, nausea, dizziness) including intensity (mild, moderate, severe)
- Presence or absence of aura
- Health Outcomes assessments

Participants will be asked to complete their eDiary at prespecified timepoints (1, 2, 3, 4, 6, 8, 24, and 48 hours) and on an event-driven basis (ie, when a headache occurs). In addition, in the double-blind treatment period, the date and time of when double-blind study intervention is taken will be captured, as well as rescue medication use.

Visit Schedule

In addition to the Screening Visit (Visit 1) and Randomization Visit (Visit 2) described above, participants will return to the clinic for the Posttreatment Visit (Visit 3) after the first qualifying prodrome event is treated, 4 days after taking double-blind study intervention. The first and second qualifying prodrome events must be 2 separate and distinct events that are at least 7 days apart. Participants unable to treat 2 qualifying prodrome events during the double-blind treatment period will be discontinued from the study.

Participants will return to the clinic for Visit 4 after the second qualifying prodrome event is treated, 4 days after taking double-blind study intervention. Visit 4 will be conducted for randomized participants who prematurely discontinue during the double-blind treatment period, regardless of whether or not they took study intervention. For additional information on study visits and procedures, please see the SoA (Section 1.3). The sequence of events during the screening and double-blind treatment periods are displayed below in Figure 4-2.

25

Figure 4-2 Screening Period

[figure not shown]
[figure not shown]

Figure 4-3 Double-blind Treatment Period

26

Efficacy, Safety, and Pharmacokinetic Assessments

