## 1.0 Introduction

This Statistical Analysis Plan (SAP) provides a technical and detailed elaboration of the statistical analyses of the efficacy and safety data as outlined and specified in the protocol of Study 3110-304-002. Study 3110-304-002 examines the efficacy, safety, and tolerability of ubrogepant in the acute treatment of migraine when administered during the prodrome. Specifications of tables, figures and data listings are contained in a separate document. The pharmacokinetics (PK) analyses will be described in a separate plan.

In general, statistical analyses will be performed using SAS version 9.4 (SAS Institute Inc., Cary, NC 27513) or higher.

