### 3.3 Other Efficacy Endpoints

Additional efficacy endpoints along with their respective clinical objectives are listed below in bullets in respect of the purposes.

To evaluate the effect of a single dose of ubrogепant (100 mg) versus placebo, administered during the prodrome, on attenuation of the headache phase:

- Absence of headache of any intensity by timepoint (1, 2, 3, 4, 6, 8, 48 hours postdose)
- Absence of moderate/severe headache by timepoint (1, 2, 3, 4, 6, 8 hours postdose)
- Absence of severe headache by timepoint (1, 2, 3, 4, 6, 8, 24, 48 hours postdose)
- Time to development of headache of any intensity within 48 hours after taking double-blind study intervention during the prodrome (Kaplan-Meier analysis)
- Time to development of headache of moderate/severe intensity within 48 hours after taking double-blind study intervention during the prodrome (Kaplan-Meier analysis)
- Time to development of headache of severe intensity within 48 hours after taking double-blind study intervention during the prodrome (Kaplan-Meier analysis)

To evaluate the effect of a single dose of ubrogепant (100 mg) versus placebo, administered during the prodrome, on prodrome symptoms, nonheadache migraine symptoms (photophobia, phonophobia, nausea, and dizziness), and aura:

- For each of the 5 most common individual prodrome symptoms:
  - Absence of any intensity at each timepoint
  - Absence of moderate/severe intensity at each timepoint
  - Absence of severe intensity at each timepoint
  - Time to absence of any intensity
- After a headache of any intensity is reported:

- Absence of nonheadache migraine symptoms (photophobia, phonophobia, nausea, dizziness) at each timepoint
- Absence of nonheadache migraine symptoms (photophobia, phonophobia, nausea, dizziness) of moderate/severe intensity at each timepoint
- Absence of nonheadache migraine symptoms (photophobia, phonophobia, nausea, dizziness) of severe at each timepoint
- Absence of aura at each timepoint

To evaluate the effect of a single dose of ubrogепant (100 mg) versus placebo on use of rescue medication:

- Rescue medication use within 24 and 48 hours after taking double-blind study intervention
- Time to rescue medication use within 48 hours after taking double-blind study intervention (Kaplan-Meier analysis)

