## **8.0 Efficacy Analyses**

### **8.1 General Considerations**

Efficacy measurement assessments are based on information recorded by the participant in an eDiary.

- Absence/Presence of and Rating of Intensity of Prodrome Symptom(s)

After experiencing each qualifying prodrome event, the absence or presence of each identified prodrome symptom(s) will be followed (up to 48 hours) and the intensity subjectively rated (mild, moderate, or severe) for those that are present.

- Absence/Presence of Headache and Rating of Headache Intensity

After the prodrome symptoms have started, the participant will be alerted to record the presence of a headache when it occurs or record the absence/presence at various timepoints (up to 48 hours) following the dose of double-blind study intervention (during the double-blind treatment period). If a headache is reported as present, the intensity will be subjectively rated (mild, moderate, or severe).

- Absence/Presence of and Rating of Intensity of Nonheadache Symptoms

The participant will record whether nonheadache symptoms (photophobia, phonophobia, nausea, and/or dizziness) were absent or present as well as the intensity (mild, moderate, or severe) of the present nonheadache symptom (up to 48 hours).

- Absence/Presence of Aura

The participant will record whether aura was present or absent (up to 48 hours).

- Health outcome assessments

The functional disability scale (FDS), a single item used to measure the participant's level of functional disability, will be used to rate the performance of daily activities using 4 response options ranging from 0 (no disability, able to function normally) to 3 (severely impaired, cannot do all or most things, bed rest may be necessary). The measure will be taken at predose (baseline) and 1, 2, 3, 4, 6, 8, 24, and 48 hours after double-blind study intervention for treating the first and second qualifying prodrome events.

Overall satisfaction with study medication for migraine will be assessed using a single-item 7-point rating scale ranging from extremely satisfied (0) to extremely dissatisfied (6). The question will be answered by the participants in their eDiary at 8 hours and 24 hours after taking double-blind study intervention for treating the first and second qualifying prodrome events.

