**Figure 6. Determination of absence of moderate/severe headache by T hours (1, 2, 3, 4, 6, 8 hours) (responder)**

**Figure 7. Determination of absence of severe headache by T hours (1, 2, 3, 4, 6, 8, 24, 48 hrs) (responder)**

The absence of a headache of any intensity by each timepoint after taking double-blind study intervention will be analyzed using the same GLMM model as primary endpoint.

Similar analyses will be performed for the absence of a headache of moderate/severe intensity and absence of severe headache by timepoint. Kaplan-Meier curves for time to development of any intensity headache (or rescue medication taken), time to development of moderate/severe headache, time to development of severe headache within 48 hours will be produced by treatment and compared between treatment using the log-rank test. In addition, Kaplan-Meier curves for time to development of moderate/severe headache (or rescue medication taken) and time to development of severe headache within 48 hours (or rescue medication taken) will be produced. Hazard ratio will be estimated from cox proportional hazard model with treatment and period factors.

For each of the 5 most common individual prodrome symptoms, the absence of any intensity, absence of moderate/severe intensity, absence of severe intensity at each timepoint will be analyzed using GLMM with additional predose baseline prodrome symptom intensity category. In addition, prodrome symptoms will be summarized by descending frequency in ubrogепant group and by intensity at predose. Same GLMM model as the primary endpoint will be performed for the absence of any intensity, absence of moderate/severe intensity, absence of severe intensity nonheadache migraine symptom at each timepoint after a headache of any intensity is reported. The absence of aura at timepoint will be analyzed using GLMM model with additional predose baseline aura status. Kaplan-Meier curves for time to absence of each of the 5 most common individual prodrome symptoms will be produced by treatment and compared between treatment using the log-rank test. Kaplan-Meier curves will also be generated censoring data collected after rescue medication for migraine associated symptoms. Hazard ratio will be estimated from cox proportional hazard model with treatment and period factors.

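### SAP 8.5 takes the hazard ratio for prodrome-symptom resolution from a Cox model on what is essentially an eight-point diary grid, without stating the event time or the tie method

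*SAP*

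**What the plan says.** SAP 3.3 lists "Time to absence of any intensity" as one of four additional endpoints for each of the five commonest prodrome symptoms. The other three are absence of any, of moderate/severe and of severe intensity at each timepoint.

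SAP 8.5 plans the analysis of the time endpoint: "Kaplan-Meier curves for time to absence of each of the 5 most common individual prodrome symptoms will be produced by treatment", with a log-rank comparison. The paragraph ends: "Hazard ratio will be estimated from cox proportional hazard model with treatment and period factors". Protocol 9.4.1.4 plans only the curves and the log-rank test for this endpoint, so the Cox model is specified in the SAP alone.

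On data collection, SAP 8.1 says "the absence or presence of each identified prodrome symptom(s) will be followed (up to 48 hours"). Protocol 4.1 gives the schedule: "Participants will be asked to complete their eDiary at prespecified timepoints (1, 2, 3, 4, 6, 8, 24, and 48 hours"). It adds entries "on an event-driven basis (ie, when a headache occurs"). Neither document describes an entry triggered by a symptom disappearing.

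SAP 1.0 states: "In general, statistical analyses will be performed using SAS version 9.4" or higher. No procedure or tie option is named. Neither document says whether a resolution is dated by the scheduled hour or by the actual entry time, or how a participant's two treated events enter the variance of the Cox model.

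**The concern.** A Cox partial likelihood is built for event times that can be ordered. Here a resolution is normally seen only at the next diary entry. A symptom that clears at 9 hours and one that clears at 23 hours are both first seen absent at 24 hours, and anything clearing in the following day is first seen absent at 48 hours. With this much grouping, the treatment of ties becomes part of the estimator. Two programmers following SAP 8.5 faithfully could report different hazard ratios and confidence limits from the same data. Headache onset and rescue medication use are less exposed, because headache entries are event-driven and rescue use is captured in the diary as it occurs.

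**Working it through.** **Inputs from the documents.** Eight scheduled diary times (Protocol 4.1); Cox model with treatment and period (SAP 8.5). The plan gives no hazard ratio, event count or resolution rate for this endpoint, so there is no planned figure to reproduce.

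**Assumed inputs.** True proportional hazards with hazard ratio (HR) 1.2, 1.3 or 1.5; nominal times; independent arms; no period effect. Four placebo curves, given as the proportion still symptomatic at 1, 2, 3, 4, 6, 8, 24 and 48 h:

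- few: .98 .96 .93 .90 .85 .80 .68 .60
- slow: .97 .94 .91 .88 .83 .78 .50 .30
- mid: .93 .86 .80 .74 .62 .50 .15 .08
- fast: .80 .63 .50 .42 .33 .27 .10 .05

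Under ubrogepant each proportion is raised to the power HR.

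**Step 1: one interval by hand.** Let q be the probability of resolving in an interval, given that the symptom was present at its start. For a single interval the Breslow score equation, d1 − (d0 + d1)·Y1·e^b / (Y0 + Y1·e^b) = 0, gives e^b = (d1/Y1)/(d0/Y0) = q1/q0. (d = resolutions, Y = number at risk, 1 = ubrogepant, 0 = placebo.) That is a ratio of probabilities, not of hazards. At true HR 1.5:

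- mid, 8-24 h: q0 = (.50 − .15)/.50 = .70; q1 = 1 − .30^1.5 = .836; ratio = 1.19.
- mid, 0-1 h: q0 = .07; q1 = 1 − .93^1.5 = .103; ratio = 1.47.
- few, 8-24 h: q0 = (.80 − .68)/.80 = .15; q1 = 1 − .85^1.5 = .216; ratio = 1.44.

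The loss is therefore worst where a large share resolves inside one interval. The complementary log-log scale does not lose it: for mid, 8-24 h, ln(1 − q1)/ln(1 − q0) = ln(.1643)/ln(.30) = 1.806/1.204 = 1.50.

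**Step 2: all eight intervals, large-sample limit at true HR 1.5.** The full score equations were solved with 20,000 per arm. Attenuation = 1 − ln(estimate)/ln(1.5).

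| Curve | Breslow HR (attenuation) | Efron HR (attenuation) | Actual entry times* |
|---|---|---|---|
| few | 1.466 (5.6%) | 1.499 (0.1%) | 1.500 |
| slow | 1.394 (18.2%) | 1.489 (1.8%) | 1.485 |
| mid | 1.351 (25.8%) | 1.463 (6.2%) | 1.465 |
| fast | 1.389 (19.0%) | 1.485 (2.5%) | 1.483 |

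*Ties broken at random, independently of arm.

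Example: mid, Breslow: 1 − ln(1.351)/ln(1.5) = 1 − .3008/.4055 = .258. At true HR 1.3 the Breslow values are 1.28, 1.24, 1.22 and 1.24, in the same order of curves. At 1.2 they are 1.19, 1.16, 1.15 and 1.16. Across all settings Breslow loses 5-26% of the log HR; Efron and actual times lose 0-6%.

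**Step 3: confidence limits (600 simulated trials per setting; 400 for complementary log-log).** With mid, 200 per arm and HR 1, the Breslow model SE is 0.104 against an empirical 0.084, and coverage is 98.7%. At HR 1.5 in the same pattern, coverage is 94% with 100 per arm, 89% with 200 and 77% with 400. In the fast pattern it is 97%, 91% and 86%. Efron coverage is 93-97% throughout. The complementary log-log model at 200 per arm returns 1.19-1.20, 1.30-1.31 and 1.49-1.50 for true HRs of 1.2, 1.3 and 1.5, with coverage 94-97%.

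**The case against.** The strongest reply is that the plan contains an omission, not an error. A reader might infer that the planned hazard ratios are biased as written. They are not necessarily so: the shrinkage needs nominal times and Breslow ties together, and the SAP commits to neither. The time of dosing is recorded in an electronic diary, so elapsed entry times may be available. SAP 1.0 also places table and figure specifications in a separate document, which may settle the tie option. This stands, and it makes the point conditional.

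The size is conditional too. Resolution rates and the number of evaluable events per symptom are not in the documents. If few symptoms resolve, even Breslow loses only 5-6%. Under-coverage appears only at larger effects and larger numbers; at HR 1.25 simulated Breslow coverage was 95-97%. Headache-triggered entries would break some ties.

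Two further inferences do not hold. One is that the trial would lose power: the planned comparison is "produced by treatment and compared between treatment using the log-rank test", and the Cox model only supplies an estimate. The other is that these hazard ratios are the sole effect sizes for the prodrome-symptom objective. Three of the four endpoints per symptom are analysed at each timepoint by a generalised linear mixed model, which uses the diary grid directly.

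Finally, an ordinary complementary log-log model treats a participant's two events as independent, as the simulations above do. With an assumed within-participant correlation of 0.5, an Efron fit gave a model SE of 0.092 against an empirical 0.067-0.073, and coverage of 98-99%. This objection stands and shapes the fix.

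**Conclusion.** The gap is real and minor. SAP 8.5 leaves the event time and tie method open for an endpoint observed essentially on eight diary times. Under one permitted combination, nominal times with Breslow ties, the log hazard ratio is attenuated by about 5-26%, with limits too wide near the null and possible under-coverage at large effects. Under Efron ties or actual entry times the attenuation is about 0-6% with near-nominal coverage. These sizes rest on the assumed resolution curves, proportional hazards and independent arms.

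The error would be towards no effect. It concerns additional endpoints outside the gatekeeping sequence in SAP 12.0, so no primary or secondary conclusion depends on it.

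**What to change.** In SAP 8.5, for time to absence of prodrome symptoms only:

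1. Fit a grouped-time proportional hazards model: binary outcome per diary interval at risk, complementary log-log link, factors for diary interval, treatment and period. The treatment coefficient is the log hazard ratio. At minimum, keep the Cox model and name Efron or exact ties.
2. State whether nominal or actual entry time defines the event, and how a resolution first seen at a headache-triggered entry is placed.
3. Use a participant-clustered (robust) variance, because each participant can contribute two events.

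Keep the Kaplan-Meier curves, the log-rank test and the timepoint models as planned.

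The cost is a few lines of SAP text and a small programming change, with no new data. The complementary log-log standard error is slightly larger than Efron's: 0.1077 against 0.1038 in the mid pattern with 200 per arm at HR 1.5, before clustering.

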Optimizing the treatment of acute migraine has been a goal of the medical community for many years and one way to do this would be to treat early, ideally before the headache begins. The CGRP receptor antagonist mechanism, a mechanism that is intrinsically preventive, suggests that ubrogepant may be a good candidate to study when administered during the prodrome, the earliest clinical manifestation of the acute migraine attack. This study is designed to examine the potential of ubrogepant, when administered during the prodrome, to prevent or attenuate the headache phase.

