Secondary 1: To evaluate the effect of a single dose of ubrogepant (100 mg) versus placebo, administered during the prodrome, on attenuation of the headache phase	1: Absence of a headache of moderate or severe intensity within 48 hours after taking doubleblind study intervention during the prodrome
2: To evaluate the effect of a single dose of ubrogepant (100 mg) versus placebo, administered during the prodrome, on ability to function normally	2: Ability to function normally over 24 hours after taking double-blind study intervention during the prodrome
3: To evaluate the effect of a single dose of ubrogepant (100 mg) versus placebo, administered during the prodrome, on prevention of the headache phase	3: Absence of a headache of any intensity within 24 hours after taking double-blind study intervention during the prodrome

19

Objectives	Endpoints	
Additional Objectives and Endpoints		
To evaluate the effect of a single dose of ubrogepant (100 mg) versus placebo, administered during the prodrome, on attenuation of the headache phase	Absence of headache of any intensity by timepoint (excluding the endpoints that are already captured as primary and secondary endpoints)	
	Absence of moderate/severe headache by timepoint (excluding the endpoints that are already captured as primary and secondary endpoints)	
	Absence of severe headache by timepoint	
	Time to development of headache of any intensity within 48 hours after taking double-blind study intervention during the prodrome (Kaplan-Meier analysis)	
	Time to development of headache of moderate/severe intensity within 48 hours after taking double-blind study intervention during the prodrome (Kaplan-Meier analysis)	
	Time to development of headache of severe intensity within 48 hours after taking double-blind study intervention during the prodrome (Kaplan-Meier analysis)	

Objectives	Endpoints
To evaluate the effect of a single dose of ubrogepant (100 mg) versus placebo, administered during the prodrome, on prodrome symptoms, nonheadache migraine symptoms (photophobia, phonophobia,	For each of the 5 most common individual prodrome symptoms:
	Absence of any intensity at each timepoint
nausea, and dizziness), and aura	Absence of moderate/severe intensity at each timepoint
	Absence of severe intensity at each timepoint
	Time to absence of any intensity
	After a headache of any intensity is reported:

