8.1. Efficacy Assessments

Efficacy measurement assessments are based on information recorded by the participant in an eDiary.

Absence/Presence of and Rating of Intensity of Prodrome Symptom(s)

After experiencing each qualifying prodrome event, the absence or presence of each identified prodrome symptom(s) will be followed (up to 48 hours) and the intensity subjectively rated (mild, moderate, or severe) for those that are present.

Absence/Presence of Headache and Rating of Headache Intensity

After the prodrome symptoms have started, the participant will be alerted to record the presence of a headache when it occurs or record the absence/presence at various timepoints (up to 48 hours) following the dose of double-blind study intervention (during the double-blind treatment period). If a headache is reported as present, the intensity will be subjectively rated (mild, moderate, or severe).

Absence/Presence of and Rating of Intensity of Nonheadache Symptoms

The participant will record whether nonheadache symptoms (photophobia, phonophobia, nausea, and/or dizziness) were absent or present as well as the intensity (mild, moderate, or severe) of the present nonheadache symptom (up to 48 hours).

50

Absence/Presence of Aura

The participant will record whether aura was present or absent (up to 48 hours).

Health outcomes assessments are described in Section 8.10.

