#### **3.2 Secondary Endpoints**

Three secondary endpoints evaluate the efficacy of ubrogepant 100 mg to prevent and attenuate the headache phase, and to assess the ability to function normally within 24 hours after taking double-blind study intervention during the prodrome:

- Absence of a headache of moderate/severe intensity within 48 hours after taking double-blind study intervention during the prodrome.
- Ability to function normally within 24 hours after taking double-blind study intervention during the prodrome.
- Absence of a headache of any intensity within 24 hours after taking double-blind study intervention during the prodrome.

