A single-item measure assessing activity limitation based on a 24-hour recall will be administered as an additional health outcome measure. The measure will be used to evaluate activity limitation with a 5-level response ranging from "Not at all limited – I could do everything" to "Extremely limited." The measure will be administered at 24 hours after taking double-blind study intervention.

The following are general considerations for efficacy analyses:

- Efficacy analyses will be performed based on mITT population.
- Continuous variables will be summarized by number of participants with observed values (n), mean, standard deviation (SD), median, 1st and 3rd quartiles (Q1, Q3), minimum (min), and maximum (max).
- Categorical variables will be summarized by number of participants with observed values or events and percentages based on the specified population.
- The efficacy analyses will be performed using a GLMM in the observed binary response variable unless an imputation method is specified.
- The least squares mean (LSMEAN) estimates of the treatment effects for the primary and secondary endpoints alongside its 95% CI will be presented.

- All statistical hypothesis tests will be performed at the 2-sided 5% significance level.
- Efficacy analyses will be presented by treatment or study intervention randomized (placebo or ubrogepant 100 mg).

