**Figure 2. Determination of absence of moderate/severe headache within 24 hours (responder)**

The primary comparison between study intervention groups will be analyzed using a GLMM model with repeated measurements based on determinable data on the primary efficacy endpoint data. The GLMM model assumes a binary distribution for the response and uses a logit link. The analysis model will include study intervention period, and treatment as categorical fixed effects. An unstructured covariance matrix will be selected for the covariance matrix of the residual effect for the repeated measurements (corresponding to the two qualifying prodrome events) within a participant. The treatment difference in terms of odds ratio between ubrogapant 100 mg and placebo will be estimated from the GLMM model.

The carryover effect will be tested although no or very minimum carryover effect is expected as the minimum 7-day washout period is much longer than the 5 times of half-life. A similar GLMM model will be fitted to examine the carryover effect. The model includes period and treatment as categorical fixed effects, and period by treatment as interaction effect. The carryover effect will be tested using the confounded period by treatment interaction at 0.05 significance level. If the carryover effect is significant, the analysis will use the first period only data for the primary efficacy analysis. For sensitivity analysis purpose, first period only data analysis will be performed regardless of the significance level of the carryover effect using logistic regression model with treatment effect.

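### Nonheadache symptoms are compared between treatments only after a post-dose headache is reported, so if ubrogepant prevents some headaches the odds ratio can mix symptom effect with selection

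*SAP*

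**What the plan says.** The nonheadache symptom endpoints are headed "After a headache of any intensity is reported" in Protocol Section 3. The same condition stands in Protocol 9.4.1.1, SAP Table 1 and SAP 3.3. The objective attached to them in Protocol Section 3 and SAP Table 1 is the effect of ubrogepant versus placebo on those symptoms.

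SAP 8.5 applies the primary endpoint's GLMM to absence of any, moderate/severe and severe symptoms, the last worded as "absence of severe intensity nonheadache migraine symptom at each timepoint after a headache of any intensity is reported". Of that model SAP 8.3.3 says: "The analysis model will include study intervention period, and treatment as categorical fixed effects". Its output is an odds ratio. On missing responses SAP 8.1 says: "The efficacy analyses will be performed using a GLMM in the observed binary response variable unless an imputation method is specified". No imputation is named for these endpoints. The SAP's estimand text covers only the primary and secondary endpoints.

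The documents differ on when the symptoms are recorded and analysed:

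- Protocol 8.1 says: "The participant will record whether nonheadache symptoms (photophobia, phonophobia, nausea, and/or dizziness) were absent or present". It follows them for up to 48 hours and names no headache condition. SAP 8.1 describes recording in the same way, and the eDiary lists in Protocol 4.1 and Section 8 carry no condition either.
- Protocol 9.4.1.4 plans the same GLMM for these symptoms without the headache condition.
- A rationale in the SAP 13.0 version history says that the eDiary collects these symptoms from the time a headache is recorded.

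**The concern.** The condition is itself an outcome of treatment. Protocol Section 2 says: "This study is designed to examine the potential of ubrogepant, when administered during the prodrome, to prevent or attenuate the headache phase". The third secondary endpoint is "Absence of a headache of any intensity within 24 hours after taking double-blind study intervention during the prodrome". Randomization makes the treatments comparable over all treated events. It does not make them comparable over the events that go on to headache, if treatment alters which events those are. At timepoint t the analysis also loses events whose headache is only delayed past t.

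Period and treatment terms do not repair this. Nor does the crossover, because a participant contributes both periods only when headache occurs in both.

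At stake is the reading of the result. A nominal odds ratio away from 1 could be reported as an effect on nausea or photophobia, for or against ubrogepant, when the drug does nothing to those symptoms once a headache has begun.

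**Working it through.** **No figure in the plan to reproduce.** The documents give no symptom rates and no current assumption for headache of any intensity. All inputs below are assumptions, chosen to show the size of the mechanism.

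**Inputs at a given timepoint t**
- f: share of placebo headaches that ubrogepant prevents or delays past t.
- q: symptom-free probability in the headaches that occur on either treatment. It is equal on both, so there is no drug effect on symptoms.
- s: symptom-free probability, on placebo, in the headaches that ubrogepant would have prevented.
- Ubrogepant causes no headache (relaxed below).

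**Formula, headache events only**
- Placebo symptom-free rate = (1 − f)q + f·s
- Ubrogepant symptom-free rate = q
- OR = odds(q) / odds((1 − f)q + f·s); above 1 favours ubrogepant. The headache rate cancels.

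Example, f = 0.2, q = 0.5, s = 0.8: placebo rate = 0.8 × 0.5 + 0.2 × 0.8 = 0.56; OR = 1 / (0.56/0.44) = 0.786.

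**Results with q = 0.5**

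| f | s = 0.8 | s = 0.65 | s = 0.5 | s = 0.3 |
|---|---|---|---|---|
| 0.1 | 0.887 | 0.942 | 1.000 | 1.083 |
| 0.2 | 0.786 | 0.887 | 1.000 | 1.174 |
| 0.3 | 0.695 | 0.835 | 1.000 | 1.273 |

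If the less symptomatic headaches are the ones prevented (s > q), the odds ratio moves against ubrogepant. If the more symptomatic ones are prevented (s < q), it moves in favour. With f = 0 or s = q it is exactly 1.

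**Other values of q**, f = 0.2 and s from q + 0.2 to q − 0.2: 0.83 to 1.22 at q = 0.3, and 0.82 to 1.20 at q = 0.7.

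**Relaxing the no-new-headache assumption.** If 10% of ubrogepant headaches are new ones with the same s, the ubrogepant rate becomes 0.9q + 0.1s. At f = 0.2 and q = 0.5 the range narrows to 0.89 to 1.08.

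**One possible value of f.** The Amendment 2 summary shows a deleted sentence with response rates of 36% on placebo and 48% on ubrogepant for the previous first secondary endpoint, which it does not name. If these are assumed to be rates of no headache within 24 hours, the headache rates are 64% and 52%, and f = (0.64 − 0.52)/0.64 = 0.1875. With q = 0.5 and s from 0.8 to 0.3 the OR is 0.80 to 1.16. With q = 0.4 and s = 0.8 the placebo rate is (0.52 × 0.4 + 0.12 × 0.8)/0.64 = 0.475 and the OR is 0.74. With q = 0.4 and s = 0.2 it is 1.17. The source text is superseded, so this is an assumption and not a planning value.

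**An all-events composite, for comparison.** Count a headache-free event as symptom absent and let h be the placebo headache rate:
- Placebo absence = 1 − h[(1 − f)(1 − q) + f(1 − s)]
- Ubrogepant absence = 1 − h(1 − f)(1 − q)

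With f = 0.2, q = 0.5 and s from 0.8 to 0.3, the OR is 1.11 to 1.39 at h = 0.2 and 1.14 to 1.52 at h = 0.6. All of that comes from headache prevention, since no symptom effect was put in.

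**The case against.** The condition is openly stated wherever the endpoint is defined, and symptom burden among attacks that reach headache is a quantity that clinicians can read. If the eDiary asked about these symptoms only once a headache was recorded, no unrestricted symptom analysis is possible. The SAP does not say how a headache-free event is coded; coding it as symptom absent would remove the selection. The values of q and s have no support in the documents, and modest ones give little: 0.94 at f = 0.1 with s only 0.15 above q. The composite carries a larger built-in shift than the analysis it accompanies, always towards ubrogepant in the illustration, and it overlaps the third secondary endpoint. Finally, these are additional endpoints.

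Much of this stands. The size is unknown, the exclusion of headache-free events is an inference, and a conditional description is legitimate. Removing nominal p-values would be largely a matter of preference; a clear label is enough.

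Two things do not fall away. The stated objective is an effect on symptoms, which the conditional odds ratio does not isolate. And if headache-free events were coded as absent, the analysis would already be the composite and would need that label. As for overlap, photophobia, phonophobia or nausea would also be analysed without the restriction if they rank among the five most common prodrome symptoms, but that is not assured, and Protocol 2.1 does not list dizziness as a prodrome symptom.

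**Conclusion.** The point holds as a minor one. The bias needs two things together: ubrogepant changes which events develop headache, and the prevented headaches would have differed in symptoms from those that remain. In the illustration with q = 0.5, the null odds ratio then lies between 0.89 and 1.08 at f = 0.1 and between 0.79 and 1.17 at f = 0.2, in a direction that cannot be known beforehand.

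A reader might infer that the SAP states that headache-free events are excluded. It does not. The wording of SAP 8.5, the observed-data rule and the version-history remark make that the most natural reading, but the denominator is unstated and Protocol 9.4.1.4 omits the condition. A reader might also infer that the analysis is known to be biased, that it favours ubrogepant, or that its false-positive rate is inflated by a definite amount. The documents give no symptom rates and no current headache assumption from which to show any of these.

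The endpoints lie outside the gatekeeping in SAP 12.0. No primary, secondary or safety conclusion depends on them, and the sample size is unaffected.

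**What to change.** 1. Keep the headache-only analysis in SAP 8.5. State its denominator at each timepoint, and label it as descriptive and not as evidence of a drug effect on symptoms.
2. Reconcile Protocol 8.1, Protocol 9.4.1.4 and SAP 8.1 with the SAP 13.0 remark on when these symptoms are recorded. If they were recorded in headache-free events, run the same GLMM on observed symptom status over all treated mITT events.
3. If they were not, add a supportive GLMM over all treated mITT events with known headache status, for *no headache accompanied by the symptom at timepoint t*, at each intensity level. Headache-free events count as absent; a headache with unrecorded symptom status stays missing. Label the result as combining headache prevention with symptom relief.

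The cost is one derivation rule and a few lines of SAP text, with no new data and no change to alpha or sample size. The downside of step 3 is that the composite cannot separate the two effects and can favour ubrogepant through prevention alone (OR about 1.1 to 1.5 in the illustration), so it should remain supportive only.
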